8.10 Trial restrictions

- No contraindications whilst on the active phase of the trial including dietary requirements/restrictions
- Due to lack of clinical data available on the use of Sambucol during pregnancy, contraception needs to be used for the 14 days duration for use and for 7 days after completion. This includes:
 - Intrauterine Device (IUD)
 - Hormonal based contraception (pill, contraceptive injection etc.)
 - Double Barrier contraception (condom and occlusive cap e.g. diaphragm or cervical cap with spermicide)
 - True abstinence

8.11 Assessment of compliance with treatment

Participants will be asked to confirm their compliance during planned telephone interviews with research staff on days 3,7,10 and 14.

9 PHARMACOVIGILANCE

9.1 Definitions

Term	Definition
Adverse Event (AE)	Any untoward medical occurrence in a participant to whom a medicinal product has been administered, including occurrences which are not necessarily caused by or related to that product.
Adverse Reaction (AR)	An untoward and unintended response in a participant to an investigational medicinal product which is related to any dose administered to that participant. The phrase "response to an investigational medicinal product" means that a causal relationship between a trial medication and an AE is at least a reasonable possibility, i.e. the relationship cannot be ruled out. All cases judged by either the reporting medically qualified professional or the Sponsor as having a reasonable suspected causal relationship to the trial medication qualify as adverse reactions. It is specifically a temporal relationship between taking the drug, the half-life, and the time of the event or any valid alternative etiology that would explain the event.
Serious Adverse Event (SAE)	A serious adverse event is any untoward medical occurrence that: 
 • results in death • is life-threatening • requires inpatient hospitalisation or prolongation of existing hospitalisation • results in persistent or significant disability/incapacity • consists of a congenital anomaly or birth defect Other 'important medical events' may also be considered serious if they jeopardise the participant or require an intervention to prevent one of the above consequences. NOTE: The term "life-threatening" in the definition of "serious" refers to an event in which the participant was at risk of death at the time of the event; it does not refer to an event which hypothetically might have caused death if it were more severe.
Serious Adverse Reaction (SAR)	An adverse event that is both serious and, in the opinion of the reporting Investigator, believed with reasonable probability to be due to one of the trial treatments, based on the information provided.
Suspected Unexpected Serious Adverse Reaction (SUSAR)	A serious adverse reaction, the nature and severity of which is not consistent with the information about the medicinal product in question set out in the reference safety information:

NB: to avoid confusion or misunderstanding of the difference between the terms "serious" and "severe", the following note of clarification is provided: "Severe" is often used to describe intensity of a specific event, which may be of relatively minor medical significance. "Seriousness" is the regulatory definition supplied above.

9.2 Operational definitions for (S)AEs

BERRY Protocol v 6.2 22.07.2021 IRAS 282732

The following adverse events are known manifestations of COVID-19 related disease. They will not be recorded in the medical notes as (S)AEs as part of this COVID-19 intervention trial.

- Chills
- Loss of taste and/or smell
- Cough
- Bloody sputum
- Sore throat
- Nasal symptoms: blocked or runny nose
- Ear pain
- Wheezing
- Chest tightness
- Shortness of breath
- Muscle aches
- Joint pain /heaviness
- Fatigue
- Headache
- Confusion
- Loss of appetite
- Abdominal pain
- Nausea/vomiting
- Diarrhoea
- Sore, red, gritty eyes
- Skin rash / irritation
- Dry/Sore lips
- Mouth Ulcers
- High Temperature

Evaluation of adverse events

The Sponsor expects that adverse events (apart from expected AEs) are recorded in the medical notes from the point of Informed Consent regardless of whether a participant has yet received a medicinal product. Individual adverse events should be evaluated by the investigator. This includes the evaluation of its seriousness, and any relationship between the investigational medicinal product(s) and/or concomitant therapy and the adverse event (causality).

Assessment of seriousness

Seriousness is assessed against the criteria in section 9.1. This defines whether the event is an adverse event, serious adverse event or a serious adverse reaction

Assessment of causality

Definitely: A causal relationship is clinically/biologically certain. **This is therefore an Adverse Reaction**

Probable: A causal relationship is clinically / biologically highly plausible and there is a plausible time sequence between onset of the AE and administration of the investigational medicinal product and there is a reasonable response on withdrawal. **This is therefore an Adverse Reaction.**

Possible: A causal relationship is clinically / biologically plausible and there is a plausible time sequence between onset of the AE and administration of the investigational medicinal product. **This is therefore an Adverse Reaction.**

BERRY Protocol v 6.2 22.07.2021 IRAS 282732

Unlikely: A causal relation is improbable and another documented cause of the AE is most plausible. **This is therefore an Adverse Event.**

Unrelated: A causal relationship can be definitely excluded and another documented cause of the AE is most plausible. **This is therefore an Adverse Event.**

Unlikely and Unrelated causalities are considered NOT to be trial drug related

Definitely, Probable and Possible causalities are considered to be trial drug related

A pre-existing condition must not be recorded as an AE or reported as an SAE unless the condition worsens during the trial and meets the criteria for reporting or recording in the appropriate section of the CRF as specified in section 9.1 and 9.2

Clinical assessment of severity

Mild: The participant is aware of the event or symptom, but the event or symptom is easily tolerated

Moderate: The participant experiences sufficient discomfort to interfere with or reduce his or her usual level of activity

Severe: Significant impairment of functioning; the subject is unable to carry out usual activities and / or the participant's life is at risk from the event.

Admissions to hospital for COVID-19 disease progression will not be reported as an SAE for the purpose of this trial as this is listed as a trial endpoint.

There are no reported risks of taking Sambucol® Original Liquid. Any adverse reaction or adverse event reported during the trial will be assessed for causality by the Investigator and appropriate reporting undertaken where necessary.

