9.3 Recording and reporting of SAEs, SARs AND SUSARs

All **SAEs** occurring from the time of start of trial treatment until 14 days post cessation of trial treatment must be recorded on the Trial data collection form and scanned and emailed to the Sponsor **within 24 hours** of the research staff becoming aware of the event. The original form will be copied and held by the Sponsor.

The Chief Investigator is responsible for ensuring that the assessment of all SAEs for relatedness and expectedness is completed and the onward notification of all SARs to the Sponsor immediately or not more than 24 hours of first notification. The sponsor has to keep detailed records of all SARs reported to them by the trial team.

All SAEs/SARs may be reported by the trial team to Pharmacare UK.

Adverse Reactions will be reported to the REC if they could:

- adversely affect the health of participants
- impact on the conduct of the trial
- alter the risk to benefit ratio of the trial
- alter the competent authority's authorisation to continue the trial in accordance with Directive 2001/20/EC

For each **SAEs** the following information will be collected:

- full details in medical terms and case description
- event duration (start and end dates, if applicable)
- action taken
- outcome
- seriousness criteria
- causality (i.e. relatedness to trial drug / investigation), in the opinion of the investigator
- whether the event would be considered anticipated.

Events will be followed up until the event has resolved or a final outcome has been reached."

BERRY Protocol v 6.2 22.07.2021 IRAS 282732

All SAEs assigned by the PI or delegate (or following central review) as both suspected to be related to treatment and unexpected will be classified as SUSARs and will be subject to expedited reporting to the REC. The sponsor will inform the REC and Manufacturer of SUSARs within the required expedited reporting timescales.”

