9.4 Responsibilities

Principal Investigator (PI):

Checking for AEs and ARs when participants attend for treatment / follow-up.

1. Using medical judgement in assigning seriousness, causality and whether the event/reaction was anticipated using the Reference Safety Information approved for the trial.
2. Using medical judgement in assigning seriousness and causality and providing an opinion on whether the event/reaction was anticipated using the Reference Safety Information approved for the trial.
3. Ensuring that all SAEs are recorded and reported to the sponsor within 24 hours of becoming aware of the event and provide further follow-up information as soon as available. Ensuring that SAEs are chased with Sponsor if a record of receipt is not received within 2 working days of initial reporting.
4. Ensuring that AEs and ARs are recorded and reported to the sponsor in line with the requirements of the protocol.

Chief Investigator (CI) / delegate or independent clinical reviewer:

1. Clinical oversight of the safety of patients participating in the trial, including an ongoing review of the risk / benefit.
2. Using medical judgement in assigning the SAEs seriousness, causality and whether the event was anticipated (in line with the Reference Safety Information) where it has not been possible to obtain local medical assessment.
3. Using medical judgement in assigning whether and event/reaction was anticipated or expectedness in line with the Reference Safety Information [in Phase I and early Phase II CTIMPs].
4. Immediate review of all SUSARs.
5. Review of specific SAEs and SARs in accordance with the trial risk assessment and protocol as detailed in the Trial Monitoring Plan.
6. Assigning Medical Dictionary for Regulatory Activities (MedDRA) or Body System coding to all SAEs and SARs.
7. Preparing the clinical sections and final sign off of the Development Safety Update Report (DSUR).

Sponsor: (NB where relevant these can be delegated to CI)

1. Central data collection and verification of AEs, ARs, SAEs, SARs and SUSARs according to the trial protocol onto a database.
2. Reporting safety information to the CI, delegate or independent clinical reviewer for the ongoing assessment of the risk / benefit according to the Trial Monitoring Plan.
3. Reporting safety information to the independent oversight committee identified for the trial Steering Committee (TSC)) according to the Trial Monitoring Plan.

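### Section 9.5 contradicts itself, 9.1, 9.3 and 9.4 on telling the sponsor about deaths; secondarily, 9.2 does not say whether its symptom exemption yields to the all-SAE rule

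*Combined protocol and SAP*

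**What the plan says.** **Deaths.** The definitions in 9.1 make any event resulting in death an SAE, and make a serious event that the reporting investigator believes is due to a trial treatment a SAR. Under 9.3, all SAEs from the start of treatment until 14 days after it stops "must be recorded on the Trial data collection form and scanned and emailed to the Sponsor" within 24 hours. Section 9.4 gives the PI the matching duty: "Ensuring that all SAEs are recorded and reported to the sponsor within 24 hours of becoming aware of the event". Section 9.5 then addresses deaths that are not a SAR or SUSAR. It has the chief investigator notify the sponsor, at once, of treatment-caused deaths and no others.

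**Listed symptoms.** Section 9.2 lists known manifestations of COVID-19 and says: "They will not be recorded in the medical notes as (S)AEs as part of this COVID-19 intervention trial". It repeats the exclusion in its general rule that "adverse events (apart from expected AEs) are recorded in the medical notes from the point of Informed Consent". The same section also says "Individual adverse events should be evaluated by the investigator", covering seriousness and causality, and later "Any adverse reaction or adverse event reported during the trial will be assessed for causality by the Investigator". It provides that a pre-existing condition is recorded or reported if it worsens and meets the criteria.

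**Admissions.** Section 9.2 has one further exemption: "Admissions to hospital for COVID-19 disease progression will not be reported as an SAE for the purpose of this trial". The reason given is that admission is a trial endpoint. Deaths are not mentioned there.

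**The concern.** Staff need one answer to two questions: whether a given death goes to the sponsor, and whether a listed symptom that turns out to be serious or suspected to be related is handled as an SAE. The protocol gives conflicting answers to the first and no clear answer to the second.

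The consequence is for safety oversight. Section 9.4 makes the sponsor responsible for "Reporting safety information to the independent oversight committee identified for the trial Steering Committee", and that committee periodically reviews safety data. Section 7.10 makes a serious safety issue a ground for stopping the trial early. An event not sent to the sponsor may not reach that review. If 9.5 is followed, a relatedness judgement made by the trial team decides whether the sponsor hears of a death at all. If the 9.2 exclusion is carried over to the SAE form, a serious listed symptom could miss SAE reporting and assessment as a possible SUSAR.

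**Working it through.** The plan states no figure to reproduce here. The check sets the sections side by side.

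**Step 1: the logic of 9.5.** Inputs: 9.1 (every death is an SAE; a death believed due to treatment is a SAR), 9.3 and 9.4 (all SAEs to the sponsor within 24 hours), 9.5 (scope: not a SAR or SUSAR; reported: treatment-caused only). A SUSAR is a kind of SAR, so it needs no separate row.

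| Death in the 9.3 window | SAR under 9.1? | In scope of 9.5? | Sponsor told under 9.5? | Sponsor told under 9.3 and 9.4? |
|---|---|---|---|---|
| Judged unrelated | No | Yes | No | Yes |
| Judged caused by treatment | Yes | No | Yes | Yes |

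No row has Yes for both scope and reporting under 9.5, so read literally the section requires notification of 0 deaths. Read by its reporting clause alone, it conflicts with 9.3 and 9.4 for every death in the first row.

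**Step 2: does another clause remove deaths from SAE reporting?** The admission exemption in 9.2 covers hospital admission for disease progression. It does not mention death, and death is not on the symptom list. The conflict in step 1 therefore stands.

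**Step 3: the 9.2 list.** Counting from chills to high temperature gives 24 items; the protocol states no count. The exclusion is worded for (S)AEs, so it names serious events as well as non-serious ones, and it carries no condition on seriousness or causality.

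**Step 4: 9.2 against 9.3.** The exclusion speaks of the medical notes; 9.3 speaks of the Trial data collection form. Neither refers to the other. Two readings are open:
- The exclusion limits only what is written in the notes, and 9.3 still catches every SAE.
- Section 9.2, whose title concerns operational definitions, decides what counts as an (S)AE, and 9.3 reports only what remains. Its pre-existing-condition sentence supports this, since it points to 9.1 and 9.2 for what goes in the CRF.

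The text does not choose between them.

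**Step 5: overlap with effects the protocol itself names.** Section 2.1 mentions vomiting and diarrhoea. Two listed items match that wording directly (nausea/vomiting; diarrhoea): 2/24 = 8.3%. Section 2.1 ties these effects to large amounts of raw, unripe fruit, not to this product. Section 2.1 also gives breathing difficulty and facial, lip or tongue swelling as allergy signs, and 7.5 allows for a new allergic reaction to the colouring. Swelling is not on the exempt list. Treating shortness of breath, wheezing, chest tightness or rash as possible allergy signs is a judgement, not a match of wording. The 8.3% is a share of list items; it measures neither risk nor frequency.

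**The case against.** **On 9.5.** It names a different actor (the chief investigator) and a different timescale (immediate rather than 24 hours). It could be meant as an extra urgent notice for treatment-caused deaths, with all other deaths following 9.3. That may have been the intention, but the wording does not carry it: the clause restricts reporting to treatment-caused deaths, and the scope sentence excludes those same deaths.

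**On 9.2.** A reader might infer that serious listed symptoms are bound to escape SAE reporting. The documents do not support that. Section 9.2 itself has any reported event assessed for causality, and lets a worsening pre-existing condition through if it meets the criteria. That matters because 6.1 requires participants to be symptomatic at entry. Section 7.5 has SAE causality judged as though the participant were on active product, and 9.9 sends any SUSAR to the sponsor however late it occurs. A participant who feels unwell after a dose is to contact the Research Nurse (8.7). These points reduce the objection to an ambiguity, but they do not remove it. None says which rule prevails, and the worsening clause does not reach a symptom that first arises during the trial.

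**On data loss.** A reader might also infer that the information disappears or that the efficacy result is biased. It does not follow. Symptoms and adverse events are asked about at every follow-up contact (sections 7 and 7.7), death is scored 0 on the VAS, and the date of death is recorded for admitted participants (7.8). The gap is in classification and onward reporting.

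**On admissions.** It is tempting to add a causality threshold to the exemption for COVID-19 admissions. No conflict has been shown there that calls for one.

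**Conclusion.** Section 9.5 is wrong as written. It requires notification of no death if read literally, and it contradicts 9.1, 9.3 and 9.4 for every death judged unrelated within the 9.3 window if read by its reporting clause. This assumes that the causality judgement used in 9.5 is the same one that defines a SAR in 9.1; the protocol describes no other.

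Section 9.2 is a secondary defect: 24 symptoms are excluded without an exception for new or worsened symptoms that are serious or suspected to be related, and its precedence against 9.3 is not stated. It could suppress a report, depending on which reading staff adopt. The documents give no expected rate of deaths or serious listed symptoms, so the number of events at stake cannot be estimated. The day-10 ANCOVA in 10.3.2 is not affected.

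**What to change.** - **9.5:** reconcile it with 9.1, 9.3 and 9.4 so that a single rule governs notification of deaths to the sponsor and deaths judged unrelated are not left out.
- **9.2, symptom list:** limit the exemption to listed symptoms that are non-serious and not suspected to be related to the trial liquid. Put the same limit on the carve-out for expected AEs in the general recording rule. State whether the exemption applies to the medical notes, the Trial data collection form, or both.
- **9.2, admissions:** leave the exemption for COVID-19 admissions as it is, adding only that it does not extend to deaths.

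The cost is a protocol amendment through the route in 13.10. No new data collection is needed, because symptoms and adverse events are already asked about at each of the five follow-up contacts. The downside is some extra AE entries and causality assessments, mostly for what will prove to be COVID-19 symptoms. At full recruitment there are at most 204 × 5 = 1,020 follow-up contacts at which the question could arise; the documents do not say how many would produce an entry.

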2.1 Assessment and management of risk

We anticipate this to be low risk trial given that Sambucol® Black Elderberry Original Liquid (*Sambucus nigra*) has never had reported adverse events/effects since commencing manufacture in 1991.

A thorough literature review has demonstrated there are no recorded side effects or drug interactions. Due to this it is classified as a food supplement and can be purchased freely without consultation or prescription, in food health shops and supermarkets, without limitation.

Vomiting and diarrhoea has been reported with the consumption of large volumes of raw and unripe fruit.

As with any product there is a potential allergy to the ingredients, hence those with known allergy will be excluded. As with all medicines, patients will be advised to seek urgent medical help if there are any signs of a severe allergy (i.e. difficulty breathing, swelling face/lips/ tongue).

With limited data on the effect in pregnancy and breast feeding this patient group has been excluded. Poorly controlled diabetics will be excluded due to the high sugar content.

The dose used is constant with no increments.

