7.5 Emergency Unblinding

In case of serious adverse event, when deemed necessary by the investigator or treating health care professional, unblinding may be requested. A designated number will be provided on hospital systems and to patients in case unblinding needs to be performed by the research team. The CI will be contactable by the research team if necessary. It is thought unlikely unblinding will need to occur unless a new allergic reaction occurs to the food colouring in the liquid.

Documentation of the unblinding process including the reason and person who performed the unblinding, will be recorded in the site file. Thereby retaining the blinding of the outcome assessors.

An alert will be placed on the patient administration system (PAS) for the trust to advise clinicians that the participant is on the BERRY trial including contact details of who to contact for unblinding in an emergency. An assessment to unblind should be made in consultation with the clinical and research teams. If the decision is made to unblind the participants randomisation to the health professional, it will be expressed that the participant should not be given this information and that it should be shared only on a need to know basis. The medical team will be advised to document the act of unblinding in the patient notes, but not the randomised arm unless this is deemed essential for the participants ongoing care. This will maintain overall blinding in the trial. The treating health care professional will continue to deal with the participant's medical emergency as appropriate.

In all cases the Investigator will evaluate the causality and expectedness of SAEs as though the participant was receiving the active medication.

Unblinding and the reasons for doing so will be recorded on the CRF/data collection tool, in the site file and medical notes. It will also be documented at the end of the trial in any final trial report and/or statistical report

The CI/Investigating team will notify the Sponsor in writing as soon as possible following the unblinding and CI/PI will also notify the relevant authorities.

SUSARs are required to be reported unblinded.

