8.7 Dosage modifications

There are no dose modifications. If a participant feels unwell after taking a dose they should contact the Research Nurse to discuss whether they should continue or stop treatment and withdraw from the trial. Research Nurse will seek advice from the Chief Investigator.

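### Section 9.2 keeps 24 COVID-19 symptoms out of (S)AE recording with no exception for suspected reactions or serious events, so suspected reactions to the liquid may drop out of the AE data

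*Combined protocol and SAP*

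**What the plan says.** Section 9.2 lists 24 symptoms attributed to COVID-19 and states: "They will not be recorded in the medical notes as (S)AEs as part of this COVID-19 intervention trial". The paragraph on evaluating events repeats the carve-out: "The Sponsor expects that adverse events (apart from expected AEs) are recorded in the medical notes from the point of Informed Consent". Neither sentence is qualified by relatedness or seriousness. Later in 9.2, hospital admission for COVID-19 progression is also kept out of SAE reporting, because it is a trial endpoint.

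Other sections bear on the same events:

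- Section 9.1 says that cases judged by the reporting professional or the sponsor as "having a reasonable suspected causal relationship to the trial medication qualify as adverse reactions". The causality scale in 9.2 counts even a possible link as an adverse reaction.
- Section 9.3 says that all SAEs from the start of treatment "until 14 days post cessation of trial treatment must be recorded on the Trial data collection form". It does not mention the 9.2 list.
- Section 9.2 also says: "Any adverse reaction or adverse event reported during the trial will be assessed for causality by the Investigator and appropriate reporting undertaken where necessary".
- Section 8.7 says: "If a participant feels unwell after taking a dose they should contact the Research Nurse to discuss whether they should continue or stop treatment".
- Sections 7 and 7.7 provide for a symptom check and a separate adverse-event question at every follow-up contact (days 3, 7, 10, 14 and 28), with a symptom check also on Day 1.
- Section 7.4 leaves investigators and the research delivery team unblinded.
- Section 10.7 names an ITT population for safety but no safety variable or method. Section 10.3 defers detail to a full SAP.

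**The concern.** Exempting ordinary disease symptoms from AE forms is sensible in a COVID-19 trial. The difficulty is that the exemption is unconditional, and the exempt terms include the ones by which intolerance of, or allergy to, an oral syrup would show itself. Each participant takes 60 ml a day of a liquid that is 70% glucose syrup (8.1, 8.6), so gastrointestinal tolerability is a natural question. Section 2.1 tells participants to "seek urgent medical help if there are any signs of a severe allergy (i.e. difficulty breathing, swelling face/lips/ tongue", and shortness of breath and wheezing are both exempt terms.

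At stake is the completeness of the AE data. If an investigator thinks that a bout of diarrhoea or a rash is possibly due to the liquid, the plan gives no clear instruction to record it. Expedited reporting under 9.3 depends on an event first being recognised and recorded as an SAE, so uncertainty at that first step carries forward. The primary efficacy analysis is not affected.

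**Working it through.** **1. The list.** Counting the bullets in 9.2 from chills to high temperature gives 24. Six are the gastrointestinal, skin and breathing terms of interest: nausea/vomiting, diarrhoea, abdominal pain, skin rash / irritation, wheezing and shortness of breath.

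**2. Applying the rules to three cases.**

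| Case | 9.2 list | Other text | Result |
|---|---|---|---|
| Diarrhoea, not suspected, not serious | Not recorded as an AE | Symptom check collects it | Intended; no problem |
| Rash, possibly related, not serious | Not recorded as an AE | 9.1 and the causality scale make it an adverse reaction | Classified as a reaction, with no stated instruction to record it |
| Life-threatening wheeze | Not recorded as an (S)AE in the medical notes | 9.3: every SAE goes on the trial form | Ambiguous |

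**3. Do other routes close the gap?**
- The adverse-event question at each contact (7, 7.7) elicits events, but 9.2 tells staff which answers not to record as such.
- The causality sentence in 9.2 covers reported events, but does not say that a listed term counts as one.
- Section 8.7 sends the participant to the nurse and sets no recording rule.
- Section 9.3 sends certain adverse reactions to the ethics committee, and 9.4 makes the PI check for AEs and ARs and ensure that they are recorded and reported as the protocol requires. The protocol includes the 9.2 list.

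None of these says that a listed term is then recorded.

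**4. Is the comparison planned elsewhere?** Section 3 covers the wellness VAS, hospital admission and HDU/ITU admission. Section 10 covers baseline summaries by arm, ANCOVA of the VAS, and chi-square tests of categorical secondary endpoints. Neither specifies a by-arm table of follow-up symptoms.

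**5. What such a table could show.** The per-arm number comes from 10.1. With SD 20, difference 10, two-sided 5% (sidedness assumed) and 90% power, the normal approximation gives 2 × (1.960 + 1.282)² × 20² / 10² = 84.1, so 85. The t-test version gives 85.03, so 86, which matches the plan. Then 86 / 0.85 = 101.2, so 102 per arm and 204 in total, also matching.

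Symptom rates are not in the documents, so these are assumed and equal in both arms. For an observed difference of zero, the Newcombe 95% half-width is √[(p − l)² + (u − p)²], where l and u are the Wilson limits for one arm. Example: 9/86 gives p = 10.47%, l = 5.60%, u = 18.71%, so √(4.87² + 8.24²) = 9.6 points.

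| Assumed rate (about) | 86 per arm (events) | 102 per arm (events) |
|---|---|---|
| 5% | ±7.3 (4) | ±6.7 (5) |
| 10% | ±9.6 (9) | ±8.5 (10) |
| 20% | ±11.9 (17) | ±10.9 (20) |
| 30% | ±13.5 (26) | ±12.5 (31) |

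If 20% already had the symptom on Day 1 (assumed), about 86 × 0.8 = 69 per arm would be at risk, and the half-widths become ±8.2, 10.7, 13.4 and 15.1 points.

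**6. What the symptom check would catch.** It asks about current symptoms. Suppose an episode starts on a random day from 1 to 14 and contacts fall exactly on days 3, 7, 10 and 14, ignoring the ±1 day window. A 1-day episode is then current at a contact for 4 of 14 start days (29%), a 2-day episode for 8 of 14 (57%) and a 3-day episode for 12 of 14 (86%).

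**The case against.** The strongest case on the other side is that the plan can be followed without contradiction. Section 9.1 defines terms and says nothing about recording, so an event may be an adverse reaction and still be exempt. Section 9.2 speaks of the medical notes and 9.3 of the trial data collection form, so both can be obeyed literally. Staff also have several other routes by which a reaction could surface.

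Much of this stands. The mismatch with 9.1 is a gap rather than a contradiction. The mismatch with 9.3 is an ambiguity, though the words about recording as (S)AEs, under a heading on operational definitions, favour the broader reading. The other routes mean that reactions may be missed, not that they will be.

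Three stronger readings are tempting and should not be adopted:

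- *That allergic reactions are excluded.* The list holds symptoms. Allergic reaction as a diagnosis, and swelling of the face, lips or tongue, are not on it. Nor does 7.5 present allergy as a likely event: "It is thought unlikely unblinding will need to occur unless a new allergic reaction occurs to the food colouring in the liquid". By 8.1 the added colourants are in the placebo only.
- *That no by-arm safety comparison will be made.* Section 10.3 defers to a SAP still to be written, 10.7 foresees a safety analysis by randomised group, and Section 1 says in general terms that the groups will be compared on symptom resolution. What can be said is that Sections 3 and 10 specify no such table.
- *That the symptom data are lost.* They are collected at every contact.

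A further fair point concerns the remedy. With unblinded staff, recording triggered by investigator suspicion can differ by arm. Section 7.5 asks for causality of SAEs to be judged as if the participant were on active treatment, but does not extend this to non-serious events.

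**Conclusion.** The point holds in a limited form and should be addressed. The 9.2 exemption is categorical, and no other text restores a listed symptom that is suspected to be related or is serious. Non-serious suspected reactions may therefore be absent from the AE data, and the instruction for serious listed events is unclear. COVID-19 progression admissions are not part of the problem, since they are captured as an endpoint.

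The size is 24 exempt terms, six of them directly relevant to tolerability or allergy. The documents do not allow an estimate of how many reactions would be missed, and the interval widths above do not measure harm. They show only that a by-arm table could exclude large differences but not small ones, under assumed rates and either 86 or 102 per arm. The conclusion about 9.2 rests on the text alone and does not depend on those assumptions.

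**What to change.** Add to 9.2: *A listed symptom that the investigator suspects is related to the liquid, that leads to stopping the liquid, or that meets a seriousness criterion (other than admission for COVID-19 progression) will be recorded as an AE or SAE and assessed for causality as though the participant were receiving the active liquid.*

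Timing after a dose should not be a trigger. With four doses a day, ordinary cough, headache or fatigue would often qualify.

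In the SAP, specify a table by arm of the six gastrointestinal, skin and breathing symptoms that are absent on Day 1 and reported at day 3, 7, 10 or 14, taken from the symptom check, with risk difference and 95% CI. It does not depend on an investigator's suspicion, so it helps to offset uneven AE recording by unblinded staff. Two cautions belong with it. Both liquids contain 70% glucose syrup, so similar rates do not exclude sugar-related effects. The placebo has its own colourants and flavouring, so a difference may come from the placebo.

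The cost is one sentence, a few extra AE forms and one table from data already collected. Unsuspected, non-serious listed symptoms that do not lead to stopping stay exempt. The table has limits: counting only new symptoms ignores worsening of existing ones, and short episodes between contacts are missed. Asking about symptoms since the last contact would deal with the second limit.
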